4.1.4 Target Accrual and Study Duration

Eight patients in the Phase I (Cohort 0), and 18 patients will be enrolled in the Phase II Cohort A (8 already enrolled under Phase 1 portion of Cohort A from previous protocol version) and 39 in Cohort B (65 patients total). It is expected to have up to 32 patients enrolled from accompanying external sites and the remainder enrolled from Roswell Park. Accrual is expected to take up to 10 years.

Patients will be drawn from the interventional pulmonology practice and from referrals from medical oncologists. All patients will come off study at 24 weeks.

Enrolled patients who do not receive the I-PDT and/or PDT for any reason (such as patient withdrawal, safety or inability to deliver the I-PDT) will be replaced.

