8.1.3 Days Prior to the EBUS Guided I-PDT Procedure

- All participants will have a blood draw for CBC with automated differentials and CMP within 2 days prior to administration of porfimer sodium. Additionally, patients on chemotherapy will have a blood draw within 2 days for CBC and CMP prior to PDT.
- For all participants: systemic administration of 2 mg/kg porfimer sodium 48 ± 4 hours (Day -2) prior to I-PDT as described in Section 6.1.1.
 - Blood draw for immune biomarkers prior to the administration of the porfimer sodium.
 - For Cohort B participants only: standard of care palliative radiotherapy of 8 Gyx1 will be administered to the target tumor at day -2 just before systemic administration of 2 mg/kg porfimer sodium. This will be coordinated with the radiation oncologist.

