10.1.3 Reporting Adverse Events

Table 2Guidelines for Routine Adverse Event Reporting for Phase 2 Studies
(Regardless of Expectedness)

Routine AEs occurring between the start date of intervention until 30 days after the last intervention, or until the event has resolved, the study participant is lost to follow-up, the start of a new treatment, or until the study investigator assesses the event(s) as stable or irreversible, will be reported. New information will be reported after it is received.

Adverse events will be graded from 1 to 5. Mild and moderate side effects are common after therapeutic bronchoscopy for central airway tumors. Therefore, grade 3 or above will be included in safety analysis, and grades 1 and 2 will be collected and reported.

Serious Adverse Events

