12.1.2 Primary Cohort 0 Phase I Safety Analysis

For patients LALC or other malignancies in the central airway that may extend and involve the esophagus. For Cohort 0, the safety profile will be measured by recording I-PDT and/or PDT treatment related AEs that are \geq grade 4 with attribution of 'possible', 'probable', or 'definite', according to the NCI CTCAE v5.0. The safety measures will be evaluated in all patients who received I-PDT and/or PDT following bronchoscopic intervention for malignant airway obstruction. Let *p* represent the proportion of the evaluable population of interest who experience an AE \geq grade 4. A true response of more than $p_0=0.20$ is considered unacceptable and evidence of such will deem the treatment unsafe for further study.

The null and alternative hypotheses to be tested are:

$$\begin{split} H_0: p &\leq p_0, \\ H_a: p > p_0. \end{split}$$

The study design stops early for evidence of safety and will proceed in two stages:

- Stage 1: If 0 out of the first 3 evaluable participants have an I-PDT and/or PDT treatment related AE≥ grade 4 (with attribution of 'possible', 'probable', or 'definite'), it will be concluded that the therapy is safe and the study will enter the Phase II component. Otherwise, the study will progress to the second stage.
- Stage 2: We will accrue 3 additional evaluable participants. If 3 or more of the total of 6 evaluable participants will have I-PDT and/or PDT treatment related AE≥ grade 4 (attribution of 'possible', 'probable', or 'definite'), it will be concluded that *p* exceeds and that the therapy is unsafe; otherwise, it will be concluded that the therapy is safe and enter the Phase II component.

The nominal significance level of this design is α =0.10.

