12.1.8 Safety Monitoring (Cohort A and Cohort B)

Safety and tolerability will be assessed by incidence, severity, and changes from baseline of all relevant parameters including adverse events (AEs), laboratory values and vital signs.

Vital sign results (systolic and diastolic blood pressure, pulse, respiration, and temperature) will be summarized descriptively for each scheduled and unscheduled protocol time point. Changes will be calculated relative to the assessments at baseline.

The changes in hematology, chemistry, and other laboratory values will be summarized descriptively for each scheduled and unscheduled protocol assessment time point. Changes will be calculated relative to the values collected at baseline. Data listings of all laboratory data collected during the study will be presented. Laboratory values outside normal limits will be identified in data listings and will include flags for high and low values.

The frequency of toxicities will be tabulated by grade. All participants who receive any study treatment will be considered evaluable for toxicity.

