12.1.9 Safety Monitoring Lead-In (Cohort B)

The safety profile will be measured by recording treatment related AEs that are \geq grade 4 with attribution of 'possible', 'probable', or 'definite', according to the NCI CTCAE v5.0. The safety measures will be evaluated in all patients who received image-guided I-PDT preceded by standard of care p-XRT of 8 Gy x1 for the treating their MCAO. The following decision rules will be followed: (i) If 0/3 AE \geq grade 4's are observed it will be concluded the therapy is safe. (ii) If 1/3 AE \geq grade 4's are observed, enroll 3 more patients for safety evaluation. If 1/6 AE \geq grade 4's are observed it will be concluded the therapy is safe. If \geq 2/6 AE \geq grade 4's are observed it will be concluded that therapy is unsafe. We calculated via Monte Carlo simulation that if the AE \geq grade 4 rate is 20%, 30% and 40% the respective probabilities of declaring the treatment unsafe are 0.26, 0.51 and 0.70.

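### Cohort B safety lead-in: at a 20% event rate the written rule declares the therapy unsafe with probability 0.29, not the printed 0.26

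*Combined protocol and SAP*

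**What the plan says.** Section 12.1.9 counts treatment-related adverse events of grade 4 or higher, attributed as possible, probable or definite. With none in the first three patients, the therapy is declared safe. With one in three, the instruction is "grade 4's are observed, enroll 3 more patients for safety evaluation". One event in six is then safe, and two or more in six is unsafe.

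The section reports the rule's behaviour from a Monte Carlo simulation: if the event "rate is 20%, 30% and 40% the respective probabilities of declaring the treatment unsafe are 0.26, 0.51 and 0.70". It does not give the number of runs. These three probabilities are the only operating characteristics stated for this rule.

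**The concern.** The rule involves at most six patients, so its operating characteristics can be written down exactly. The value at 20% does not match the printed one, while the values at 30% and 40% do, to within rounding or simulation error.

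This is Cohort B's only numeric safety rule. Section 12.1.8 is descriptive, and Section 11 provides for annual committee review without a numeric boundary. Section 6.1.10 says that the risk of giving I-PDT two days after palliative radiotherapy is unknown. The rate of 20% is also the threshold used for Cohort 0 in Section 12.1.2. A committee judging whether the lead-in is strict enough should have the correct figure at that rate.

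**Working it through.** **Inputs, all from Section 12.1.9.** Safe at 0/3; three more patients at 1/3; safe at 1/6; unsafe at 2/6 or more; true event rates p of 0.20, 0.30 and 0.40; printed probabilities of 0.26, 0.51 and 0.70. Outcomes 2/3 and 3/3 are counted as unsafe, because the total is then already at least two whatever follows.

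**Formula.** The therapy is declared safe in two ways:

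- no event in the first three: (1−p)³;
- one event in the first three and none in the next three: 3p(1−p)² × (1−p)³ = 3p(1−p)⁵.

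Hence P(unsafe) = 1 − (1−p)³ − 3p(1−p)⁵.

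**Results against the printed figures.**

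| p | (1−p)³ | 3p(1−p)⁵ | P(unsafe), exact | Printed | Printed − exact |
|---|---|---|---|---|---|
| 0.20 | 0.5120 | 0.1966 | 0.2914 | 0.26 | −0.031 |
| 0.30 | 0.3430 | 0.1513 | 0.5057 | 0.51 | +0.004 |
| 0.40 | 0.2160 | 0.0933 | 0.6907 | 0.70 | +0.009 |

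The 30% figure is reproduced after rounding and the 40% figure is within 0.01. A simulation of 2,000,000 runs gives 0.2913, 0.5060 and 0.6906. Solving the formula for 0.26 gives p = 0.185, so the printed value belongs to a true rate of 18.5%.

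**Other readings of the rule.**

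| Reading | 20% | 30% | 40% |
|---|---|---|---|
| Any non-zero count goes to six, then ≥2/6 unsafe | 0.291 | 0.506 | 0.691 |
| 2/3 and 3/3 not counted as unsafe | 0.187 | 0.290 | 0.339 |
| 2/3 and 3/3 left out of the denominator | 0.209 | 0.370 | 0.523 |
| Only 3/3 counted as unsafe at the first stage | 0.195 | 0.317 | 0.403 |
| Six enrolled at once, ≥2/6 unsafe | 0.345 | 0.580 | 0.767 |
| Cohort 0 rule of Section 12.1.2 | 0.095 | 0.246 | 0.442 |
| ≥2/3 unsafe; after 1/3, ≥3/6 unsafe | 0.144 | 0.311 | 0.504 |
| ≥2/3 unsafe; after 1/3, only exactly 2/6 unsafe | 0.252 | 0.411 | 0.539 |
| Fixed five patients, ≥2/5 unsafe | 0.263 | 0.472 | 0.663 |

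The first row equals the main reading. The last two come near 0.26 at 20% but miss at 30% and 40%. None gives 0.26, 0.51 and 0.70 together.

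**Could it be simulation noise?** The number of runs N is an assumption, since the plan gives none. Taken alone, the 20% figure has standard error √(0.2914 × 0.7086 / N), which is 0.0144 at N = 1,000, so 0.26 lies 2.2 standard errors low. But it is the worst of three figures, so a joint test is fairer. It sums the three squared standardised differences and refers the total to chi-square on 3 degrees of freedom, assuming independent runs at each rate. The last column reduces each gap by 0.005 (to zero if it is smaller) to allow for rounding to two decimals.

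| Runs | Chi-square | P-value | P-value allowing for rounding |
|---|---|---|---|
| 500 | 2.63 | 0.45 | 0.63 |
| 1,000 | 5.25 | 0.15 | 0.33 |
| 1,500 | 7.88 | 0.049 | 0.16 |
| 5,000 | 26.26 | <0.0001 | 0.0006 |

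Noise is a tenable explanation at about 1,000 to 1,500 runs and is clearly excluded only at several thousand.

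**The case against.** The strongest reply is that the printed figures are presented as simulated estimates, and a simulated estimate need not equal the exact value. With the run count unstated, the text cannot show whether 0.26 is a mistake or a coarse simulation. That stands, and it rules out calling the figure a proven programming or transcription error. It does not rescue the figure: a simulation coarse enough to produce 0.26 cannot support two decimals, and the exact value comes from one line of algebra.

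The second reply is that little depends on the number. No boundary, sample size or analysis uses it, and the discrepancy is in the harmless direction. That also stands, and it sets the severity.

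Two stronger inferences are tempting, and the documents do not support them as defects.

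- **That the rule leaves 2/3 and 3/3 undecided.** No line names these outcomes, but two events already meet the 2/6 boundary, so the verdict is fixed. Section 12.1.9 adds patients only after 1/3. The Cohort 0 wording, "Otherwise, the study will progress to the second stage", belongs to a completed cohort with a different boundary. P(unsafe) is the same under either practice.
- **That severe events before illumination escape the safety rule.** Section 12.1.9 says "The safety measures will be evaluated in all patients who received image-guided I-PDT preceded by standard of care p-XRT", and Section 12.1.8 says "All participants who receive any study treatment will be considered evaluable for toxicity". These can be read together: the lead-in judges the combination whose risk is unknown, while Section 12.1.8 governs general toxicity tables. Serious events are reportable from consent (Section 10.1.5), the monitoring committee can recommend suspension or termination (Section 11), and the study can be ended at once for safety (Section 15.1.2). Whether such a patient should count is a separate question of unknown size, with no bearing on the arithmetic.

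**Conclusion.** The concern holds as a minor numerical correction. For the rule as written, the probability of declaring the therapy unsafe at a true rate of 20% is 0.291 against 0.26 printed, a gap of 0.031. At 30% the printed figure is right after rounding; at 40% it is 0.01 above the exact 0.69, within plausible simulation error. The true rule is slightly more likely to declare the therapy unsafe at 20% than the plan says, so a reader relying on 0.26 would underrate its caution a little.

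The conclusion assumes that patients' events are independent with a common rate, and that 2/3 and 3/3 mean unsafe, which the 2/6 boundary implies and the printed 30% and 40% figures support. It needs no assumption about the number of simulation runs. That number bears only on how the discrepancy arose, which the documents do not settle.

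**What to change.** In Section 12.1.9, replace the simulated probabilities with the exact 0.29, 0.51 and 0.69, and say that they are exact binomial values rather than simulation results. Two printed figures change (0.26 to 0.29, and 0.70 to 0.69) and 0.51 stays. The decision rule, the sample size and the data collected are unaffected, and the only cost is a wording change at the next amendment.

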13 ETHICAL AND REGULATORY STANDARDS

13.1.1 Ethical Principles

Roswell Park will be the IRB of record for this multi-site study. Accruals will occur at Roswell Park Cancer Institute and accompanying external sites. Any participating site will enter into a reliance agreement with the Roswell Park IRB and proper IRB approval of each site will be given prior to participation in the study.

This study will not be initiated until the protocol and informed consent document(s) have been reviewed and approved by a properly constituted Institutional Review Board (IRB) or Independent Ethics Committee (IEC). Each participant (or legal guardian) shall read, understand, and sign an instrument of informed consent prior to performance of any study-specific procedure. It is the responsibility of the investigator to ensure that the participant is made aware of the investigational nature of the treatment and that informed consent is given.

The Investigator is responsible for the retention of the participant log and participant records; although personal information may be reviewed by authorized persons, that information will be treated as strictly confidential and will not be made publicly available. The investigator is also responsible for obtaining participant authorization to access medical records and other applicable

study specific information according to Health Insurance Portability and Accountability Act regulations (where applicable).

This study will be conducted in compliance with all applicable laws and regulations of the state and/or country and institution where the participant is treated. The clinical trial should be conducted in accordance with the ethical principles embodied in the Belmont Report: Ethical Principles and Guidelines for the Protection of Human Subjects of Research, consistent with good clinical practice and the applicable regulatory requirements and according to the guidelines in this protocol, including attached appendices.

13.1.2 Informed Consent

The Investigator (or IRB specified designee) is responsible for obtaining written consent from each participant in accordance with GCP guidelines using the approved informed consent form, before any study specific procedures (including screening procedures) are performed. The informed consent form acknowledges all information that must be given to the participant according to applicable GCP guidelines, including the purpose and nature of the study, the expected efficacy and possible side effects of the treatment(s), and specifying that refusal to participate will not influence further options for therapy. Any additional information that is applicable to the study must also be included. Additional national or institutionally mandated requirements for informed consent form, processing of sensitive clinical trial data and transfer to other countries for further processing is allowed.

The Investigator shall provide a copy of the signed consent form to the participant and the signed original shall be maintained in the Investigator File. A copy of the signed consent form must be filed in the participant research file. At any stage, the participant may withdraw from the study and such a decision will not affect any further treatment options.

14 STUDY RESPONSIBILITIES

14.1.1 Data Collection

Cohorts A and B patient-reported outcomes from questionnaires will be stored using the secure Roswell Park REDCap database, while the CTMS will be used to collect physician-assessed clinical outcomes.

Patient survey data will be kept on the secure Roswell Park REDCap database, and will be accessible only by the PI, Co-Investigator, and the CRS representative. Patient clinical data will be kept in CRS CTMS. The REDCap database will be password protected. All records will be kept in a limited access environment. All computer entry and networking programs will be done using PIDs only.

Full build studies are managed by Roswell Park CRS Data Management for analysis by Roswell Park Biostatisticians. All electronic case report form (eCRF) data are captured for these studies.

Data management activities will be performed using eClinical. eClinical is a suite of software tools that enables the collection, cleaning and viewing of clinical trial data. CRS data management will design the study-specific database and facilitate its development by the eClinical Information Technology team. Once the database design is approved by the Investigator, Statistician, and Clinical Research Coordinator, the database will be put into production and data entry can begin.

Data can be entered and changed only by those with the rights to do so into the eCRFs.

14.1.2 Maintenance of Study Documents

Essential documents will be retained per Roswell Park's policy for 6 years from the study termination date. These documents could be retained for a longer period, however, if required by the applicable local regulatory requirements or by an agreement with Roswell Park.

15 ADMINISTRATIVE RULES

15.1.1 Revisions to the Protocol

Roswell Park may make such changes to the protocol as it deems necessary for safety reasons or as may be required by the U.S. FDA or other regulatory agencies. Revisions will be submitted to the IRB/ERC for written approval before implementation.

15.1.2 Termination of the Study

It is agreed that, for reasonable cause, either the Roswell Park Investigators or the Sponsor, may terminate this study, provided a written notice is submitted within the time period provided for in the Clinical Trial Agreement. In addition, Roswell Park may terminate the study at any time upon immediate notice if it believes termination is necessary for the safety of participants enrolled in the study.

15.1.3 Confidentiality

Any data, specimens, forms, reports, video recordings, and other records that leave the site will be identified only by a participant identification number (Participant ID, PID) to maintain confidentiality. All records will be kept in a limited access environment. All computer entry and networking programs will be done using PIDs only. Information will not be released without written authorization of the participant.

Completed Cohort A and B participant questionnaire data will be entered into a secure REDCap Database on the Roswell Park server via tablet by the patient, or the usage of paper questionnaires when tablets are unavailable (paper questionnaire information will then be entered by the study Clinical Research Coordinator). This will be accessible only to investigators on the study. For analysis, data will be entered into OnCore which will only be accessible to authorized individuals. Any paper files containing identifiers will not be taken off Roswell Park premises. PHI will not be reused or disclosed to any other person or entity.

16 APPENDICES

Description	Status
Fully active, able to carry on all pre-disease performance without restriction.	0
Restricted in physically strenuous activity but ambulatory and able to carry out work of a light or sedentary nature, e.g., light housework, office work.	1
Ambulatory and capable of all self-care but unable to carry out any work activities.	2
Capable of only limited self-care, confined to bed or chair more than 50% of waking hours.	3
Completely disabled. Cannot carry on any self-care. Totally confined to bed or chair.	4
Dead	5

Appendix C Instructions for Multi-Site Studies – can enroll patients into Cohorts A and B only

1. CONTACT INFORMATION

All questions related to the protocol or study implementation should be directed to:

Roswell Park Comprehensive Cancer Center CRS Quality Assurance (QA) Office [contact] [name] **Telephone:** Monday - Friday; 8:00 AM to 4:30 PM EST [contact] After hours, weekends, and holidays request the Roswell Park Investigator [contact]

2. INFORMED CONSENT

- Informed consent must be obtained by the site Investigator/designee from any participants wishing to participate, prior to any procedures or treatment.
- An informed consent template is provided by Roswell Park and can be amended to reflect institutional requirements.
- All consent changes **must** be reviewed by Roswell Park CRS QA Office prior to submission to the site IRB.
- The informed consent must be IRB approved.
- Always check that the most up to date version of the IRB approved consent is being used.
- Within 5 business days, notify the Roswell Park CRS QA Office of all participant withdrawals or consent to limited study participation and appropriately document the discontinuation and the reason(s) why.

3. PARTICIPANT REGISTRATION

The participant completes the Gender, Race, and Ethnicity Form and this is placed in the study binder.

Roswell Park does not grant exceptions to eligibility criteria.

Phase 2 Protocol Registration Instructions

The Subject Screening and Enrollment Log must be emailed ([contact]) to the Roswell Park CRS QA Office within 1 business day of the date the participant is consented. Once the Investigator has determined that eligibility has been met, complete the eligibility check list and email it to the Roswell Park CRS QA Coordinator at [contact].

Protocol Randomization Instructions

Patients at Roswell Park Cancer Institute will be registered directly by Roswell staff using the web-based registration system. For patients at institutions outside Roswell Park Cancer Institute,

the local site staff will contact the appropriate coordinator to register the patient using the webbased registration application as developed by the GOG Foundation Statistical & Data Management Center in conjunction with the study biostatistician. Within 24 hours the QA Coordinator will email the randomization arm assignment and participant ID # back to the site PI. The site PI will send a confirmation email back to the QA Coordinator verifying the randomization arm for the specified network participant. Questions regarding randomization issues can be emailed to [contact].

4. STUDY DEVIATIONS

- If a deviation has occurred to eliminate hazard, this must be reported to the Roswell Park CRS QA department, site IRB and any other regulatory authority involved in the study.
- ALL study deviations will be recorded on the **Study Deviation Log**.
- Participants inadvertently enrolled with significant deviation(s) from the study-specified criteria will be removed from the study, at the discretion of the Principal Investigator.

5. STUDY DOCUMENTATION

- Study documents must be filled out completely and correctly. Ditto marks are not allowed.
- If an entry has been documented in error put a single line through the entry and initial and date the change. The Roswell Park CRS QA Coordinator must be able to read what has been deleted.
- Do **NOT** use white-out, magic marker, scratch-outs.
- Do **NOT** erase entries.
- Use only black ink for documentation on the accountability form and any other study forms.
- It is the responsibility of Roswell Park to inform the Investigator/ institution as to when these documents no longer need to be retained. If, for any reason, the Investigator desires to no longer maintain the study records, they may be transferred to another institution, another investigator, or to Roswell Park upon written agreement between the Investigator and Roswell Park.

6. **DRUG ACCOUNTABILITY**

Drug accountability must be strictly maintained.

- Responsibility rests solely with the Investigator but can be delegated as appropriate (e.g., to pharmacy personnel).
- A drug accountability record form (DARF) will record quantities of study drug received, dispensed to participants and wasted, lot number, date dispensed, participant ID number and initials, quantity returned, balance remaining, manufacturer, expiration date, and the initials of the person dispensing the medication.
- Study drug supply will only be used in accordance with the IRB approved study.
- Drug accountability forms are protocol and agent specific; they are study source documents and will be used to verify compliance with the study.

- An inventory count must be performed with each transaction. Any discrepancies shall be documented and explained.
- Drug accountability forms must be stored with study related documents.
- Each medication provided for this study and each dosage form and strength must have its own DARF.
- Dispensing the wrong study supply is considered a medication error.
- **NEVER** replace investigational agents with commercial product.
- Do **NOT** "transfer", "borrow" or "replace" supplies between studies.

7. SERIOUS ADVERSE EVENT REPORTING

The site Investigator or designated research personnel will report all SAEs, whether related or unrelated to the investigational agent(s) to the **IRB in accordance with their local institutional guidelines**. The site will notify the Roswell Park CRS QA Coordinator within 1 business day of being made aware of the SAE. A preliminary written report must follow within 1 business day of the first notification using the following forms:

- Roswell Park Oncore SAE form
- Notify Pinnacle Biologics Inc. (Contact: [name], [contact])

Name, address, phone, e-mail

The principal investigator or designee will inform Roswell (via email using both the Oncore SAE form and MEDWATCH 3500A form) within twenty-four (24) hours of first awareness of any event that meets the above criteria. Both forms should include all available information, including a brief narrative describing the SAE, attributions, and any other relevant information. Upload all related (redacted) source information into OnCore along with the completed forms signed by the Forms PI. will be submitted to the CRS OA Office via email to [contact].

A complete follow-up report must be sent to the Roswell Park CRS QA Coordinator when new information becomes available.

8. UNANTICIPATED PROBLEM REPORTING

An unanticipated problem (UP) is any incident, experience, or outcome that meets all of the criteria in **Section 17.7**.

For all adverse events occurring that are unanticipated and related or possibly related to the research drug, biologic or intervention, the participating physician or delegated research staff from each site will notify their local **IRB in accordance with their local institutional guidelines**. The site must also notify the Roswell Park CRS QA Coordinator within 1 business day of being made aware of the Unanticipated Problem by completing the **Roswell Park Unanticipated Problem Report Form** and emailing it to the Roswell Park CRS QA Coordinator to [contact].

